8.2 LIST OF AES OF SPECIAL INTEREST

Category	Adverse Event Term
	Bile output abnormal (PT)
	Bile output decreased (PT)
	Bile output increased (PT)
	Biliary cirrhosis (PT)
	Biliary colic (PT)
	Biliary dilatation (PT)
	Biliary dyskinesia (PT)
	Biliary dyspepsia (PT)
	Biliary fibrosis (PT)
	Biliary fistula (PT)
	Biliary ischaemia (PT)
	Biliary tract disorder (PT)
	Bilirubin conjugated abnormal (PT)
	Bilirubin conjugated increased (PT)
	Bilirubin excretion disorder (PT)
	Bilirubin urine present (PT)
	Bilirubinuria (PT)
	Blood alkaline phosphatase abnormal (PT)
	Blood alkaline phosphatase increased (PT)
	Blood bilirubin abnormal (PT)
	Blood bilirubin increased (PT)
	Blood bilirubin unconjugated increased (PT)
	Cholangiogram abnormal (PT)
	Cholecystectomy (PT)
	Cholecystitis (PT)
	Cholecystitis acute (PT)
	Cholecystitis chronic (PT)
	Cholecystogram intravenous abnormal (PT)
	Cholecystogram oral abnormal (PT)
	Cholelithiasis (PT)
	Cholelithiasis migration (PT)
	Cholelithiasis obstructive (PT)
	Cholestasis (PT)
	Deficiency of bile secretion (PT)
	Endoscopy biliary tract abnormal (PT)
	Gallbladder disorder (PT)
	Gallbladder enlargement (PT)
	Gallbladder fibrosis (PT)
	Gallbladder fistula (PT)
	Gallbladder hypofunction (PT)

Category	Adverse Event Term
category	Gallbladder necrosis (PT)
	Gallbladder obstruction (PT)
	Gallbladder oedema (PT)
	Gallbladder operation (PT)
	Gallbladder operation (FT)
	Haemohilia (PT)
	Henatitis cholestatic (PT)
	Hepatobiliary disease (PT)
	Hyperbilirubinaemia (PT)
	laundice (PT)
	Jaundice cholestatic (PT)
	Jaundice extrahepatic obstructive (PT)
	Obstructive pancreatitis (PT)
	Perforation bile duct (PT)
	Pseudocholelithiasis (PT)
	Ultrasound biliary tract abnormal (PT)
	Urine bilirubin increased (PT)
	X-ray hepatobiliary abnormal (PT)
AESI Growth hormone deficiency related AEs	Blood growth hormone decreased (PT)
,	Insulin-like growth factor decreased (PT)
AESI Hyperglycemia-related AEs	Blood glucose increased (PT)
	Blood insulin decreased (PT)
	Diabetes mellitus (PT)
	Diabetes mellitus inadequate control (PT)
	Diabetes with hyperosmolarity (PT)
	Diabetic coma (PT)
	Diabetic hyperglycaemic coma (PT)
	Diabetic hyperosmolar coma (PT)
	Diabetic ketoacidosis (PT)
	Diabetic ketoacidotic hyperglycaemic coma (PT)
	Diabetic ketosis (PT)
	Fructosamine increased (PT)
	Glucose tolerance decreased (PT)
	Glucose tolerance impaired (PT)
	Glucose tolerance test abnormal (PT)
	Glucose urine (PT)
	Glycosuria (PT)
	Glycosylated haemoglobin increased (PT)
	Hyperglycaemia (PT)
	Hyperglycaemic hyperosmolar nonketotic syndrome (PT)

Category	Adverse Event Term
	Impaired fasting glucose (PT)
	Impaired insulin secretion (PT)
	Increased insulin requirement (PT)
	Insulin-requiring type 2 diabetes mellitus (PT)
	Ketoacidosis (PT)
	Ketonuria (PT)
	Ketosis (PT)
	Ketosis-prone diabetes mellitus (PT)
	Monogenic diabetes (PT)
	Type 1 diabetes mellitus (PT)
	Type 2 diabetes mellitus (PT)
AESI Hypocortisolism related AEs	Adrenal insufficiency (PT)
	Adrenal suppression (PT)
	Adrenocortical insufficiency acute (PT)
	Cortisol decreased (PT)
	Cortisol deficiency (PT)
	Cortisol free urine decreased (PT)
	Glucocorticoid deficiency (PT)
	Glucocorticoids decreased (PT)
	Secondary adrenocortical insufficiency (PT)
	Steroid withdrawal syndrome (PT)
AESI Hypotension related AEs	Blood pressure ambulatory decreased (PT)
	Blood pressure decreased (PT)
	Blood pressure diastolic decreased (PT)
	Blood pressure immeasurable (PT)
	Blood pressure orthostatic abnormal (PT)
	Blood pressure orthostatic decreased (PT)
	Blood pressure systolic decreased (PT)
	Hypotension (PT)
	Mean arterial pressure decreased (PT)
AESI Hypothyroidism related AEs	Blood thyroid stimulating hormone decreased (PT)
	Hypothyroidism (PT)
	Myxoedema (PT)
	Myxoedema coma (PT)
	Secondary hypothyroidism (PT)
	Thyroid dermatopathy (PT)
	Thyroid stimulating hormone deficiency (PT)
	Thyroxine free decreased (PT)
	Tri-iodothyronine decreased (PT)
	Tri-iodothyronine free decreased (PT)

Category	Adverse Event Term
AESI Injection site reaction related AEs	Administration site abscess (PT)
	Immediate post-injection reaction (PT)
	Injection site atrophy (PT)
	Injection site bruising (PT)
	Injection site discolouration (PT)
	Injection site discomfort (PT)
	Injection site erosion (PT)
	Injection site erythema (PT)
	Injection site exfoliation (PT)
	Injection site granuloma (PT)
	Injection site haematoma (PT)
	Injection site haemorrhage (PT)
	Injection site hypersensitivity (PT)
	Injection site inflammation (PT)
	Injection site irritation (PT)
	Injection site necrosis (PT)
	Injection site nodule (PT)
	Injection site oedema (PT)
	Injection site pain (PT)
	Injection site pruritus (PT)
	Injection site rash (PT)
	Injection site reaction (PT)
	Injection site swelling (PT)
	Injection site urticaria (PT)
ESI Liver safety related AEs	Alanine aminotransferase abnormal (PT)
	Alanine aminotransferase increased (PT)
	Ammonia increased (PT)
	Aspartate aminotransferase abnormal (PT)
	Aspartate aminotransferase increased (PT)
	Blood cholinesterase abnormal (PT)
	Blood cholinesterase decreased (PT)
	Computerised tomogram liver abnormal (PT)
	Gamma-glutamyltransferase abnormal (PT)
	Gamma-glutamyltransferase increased (PT)
	Guanase increased (PT)
	Hepatic enzyme abnormal (PT)
	Hepatic enzyme decreased (PT)
	Hepatic enzyme increased (PT)
	Hepatic function abnormal (PT)
	Hepatobiliary scan abnormal (PT)

Category	Adverse Event Term
	Hyperammonaemia (PT)
	Hypertransaminasaemia (PT)
	Liver function test increased (PT)
	Transaminases abnormal (PT)
	Transaminases increased (PT)
	Ultrasound liver abnormal (PT)
	Urine bilirubin increased (PT)
AESI Low blood cell related AEs	Anaemia (PT)
	Febrile neutropenia (PT)
	Haematocrit decreased (PT)
	Haemoglobin decreased (PT)
	Leukopenia (PT)
	Lymphocyte count decreased (PT)
	Lymphopenia (PT)
	Neutropenia (PT)
	Platelet count decreased (PT)
	Red blood cell count decreased (PT)
	Thrombocytopenia (PT)
AESI Pancreatitis related AEs	Abdominal compartment syndrome (PT)
	Blood trypsin increased (PT)
	Fat necrosis (PT)
	Hyperlipasaemia (PT)
	Lipase abnormal (PT)
	Lipase increased (PT)
	Pancreatic enzyme abnormality (PT)
	Pancreatic enzymes abnormal (PT)
	Pancreatic enzymes increased (PT)
	Pancreatitis (PT)
	Pancreatitis acute (PT)
	Pancreatitis haemorrhagic (PT)
	Pancreatitis necrotising (PT)
	Pancreatitis relapsing (PT)
	Peripancreatic fluid collection (PT)
AESI QT-prolongation-related AEs	Cardiac arrest (PT)
	Cardiac death (PT)
	Cardiac fibrillation (PT)
	Cardio-respiratory arrest (PT)
	Electrocardiogram QT interval abnormal (PT)
	Electrocardiogram QT prolonged (PT)
	Electrocardiogram repolarisation abnormality (PT)

Category	Adverse Event Term
	Long QT syndrome (PT)
	Loss of consciousness (PT)
	Sudden cardiac death (PT)
	Sudden death (PT)
	Syncope (PT)
	Torsade de pointes (PT)
	Ventricular arrhythmia (PT)
	Ventricular fibrillation (PT)
	Ventricular flutter (PT)
	Ventricular tachyarrhythmia (PT)
	Ventricular tachycardia (PT)

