The safety and efficacy of Pasireotide LAR was confirmed in a phase 3, multicenter, 12-month trial in which 150 patients were randomized to receive either Pasireotide 10 mg or 30 mg [SOM230G2304]. The most common adverse events were hyperglycaemia (36 [49%] in the 10 mg group and 36 [47%] in the 30 mg group), diarrhoea (26 [35%] and 33 [43%]), cholelithiasis (15 [20%] and 34 [45%]), diabetes mellitus (14 [19%] and 18 [24%]), and nausea (15 [20%] and 16 [21%]). The observed safety profile of long-acting pasireotide was consistent with that of twice-daily pasireotide in patients with Cushing's disease.

Further details on pasireotide clinical safety can be found in the [Investigator Brochure].

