Pasireotide is currently approved for use in Cushing's disease (s.c. formulation) in over 80 countries, and for use in acromegaly (i.m. LAR formulation) in over 30 countries worldwide. The safety profile of both formulations of pasireotide has been well characterized in a comprehensive development program and is similar to the established profile of SSAs, except for the higher incidence and magnitude of hyperglycemia, which is manageable with proper treatment with anti-diabetic medication. The mechanism of the pasireotide-induced hyperglycemia has been well characterized in mechanistic studies. It is primarily a consequence of decreased secretion of insulin and incretins, with no change in hepatic or peripheral insulin

sensitivity, is less severe in responders than non-responders, and is reversible upon discontinuation. The risk of hyperglycemia is minimized by monitoring of patients' FPG and HbA1c levels and appropriate management. Additional expected pharmacodynamic effects of pasireotide are well known and are primarily GI disturbances, bradycardia, mild QT prolongations, cholelithiasis and transient elevations in serum levels of transaminases. These effects can be effectively monitored and managed, as detailed in the IB and in the label. No unexpected new findings have emerged with long-term exposure to pasireotide.

Overall, pasireotide has a favorable benefit/risk profile in the discussed indications. Patients rolled-over to this study are those who have benefited from the treatment with pasireotide and continue to obtain this benefit with continuation of the treatment. The current label and IB fully characterize both efficacy and safety aspects of pasireotide, s.c. and LAR, to enable its appropriate use to maximize benefit while minimizing risks to patients. The risk to patients in this trial may be minimized by compliance with the eligibility criteria and study procedures, and close clinical monitoring. There may be unforeseen risks with pasireotide which could be serious.

3 Objectives and endpoints

Objectives and related endpoints are described in [Table 3-1](#) below.

Table 3-1 Objectives and related endpoints

Objective	Endpoint	Analysis
Primary		
To evaluate long term safety data i.e. SAEs and AEs	Frequency and severity of AEs/SAEs	Refer to Section 10.4
Secondary		

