- A single occurrence will be counted if there is ≤ 1 day gap between the end date of the preceding AE and the start date of the consecutive AE
- More than one occurrence will be counted if there is > 1 day gap between the end date of the preceding AE and the start date of the consecutive AE

For occurrence, the presence of at least one SAE / SAE suspected to be related to study treatment / non SAE has to be checked in a block e.g., among AE's in a \leq 1 day gap block, if at least one SAE is occurring, then one occurrence is calculated for that SAE.

The number of deaths resulting from SAEs suspected to be related to study treatment and SAEs irrespective of study treatment relationship will be provided by SOC and PT.

Adverse events of special interest / grouping of AEs

The specific categories of AEs of special interest list for SOM230 are listed in attachment 8.2.

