Study Procedures Criteria*	G08 Investigator failed to assess if the patient was continuing to receive clinical benefit at the visit.
Study Procedures Criteria	Investigator failed to document in eCRF if the patient was continuing to receive clinical benefit at the visit
Visit Schedule Criteria*	G10 Missed visit due to COVID-19
Visit Schedule Criteria*	G11 Visit done outside of study site due to COVID-19
Study Procedures Criteria*	G12 Assessment/ procedure changed due to COVID-19
Study Procedures Criteria*	G13 Drug supply method changed due to COVID-19
Investigation Product (IP) Compliance*	G14 Treatment not given due to COVID-19
Other Criteria*	G15 Discontinuation due to COVID-19
Study Procedures Criteria*	G16 Patient failed to adhere to protocol requirements or visit schedule
Study Procedures Criteria*	G17 Female patient of childbearing potential did not complete diary with dates and outcome of at-home urine pregnancy tests while on study treatment
Study Procedures Criteria	Site staff are allowed to work for limited hours due to Covid 19 restrictions

Category	Adverse Event Term
AESI Bradycardia related AEs	Atrial conduction time prolongation (PT)
	Atrioventricular block (PT)
	Atrioventricular block complete (PT)
	Atrioventricular block second degree (PT)
	Atrioventricular dissociation (PT)
	Bradycardia (PT)
	Central bradycardia (PT)
	Conduction disorder (PT)
	Defect conduction intraventricular (PT)
	Electrocardiogram PQ interval prolonged (PT)
	Electrocardiogram PR prolongation (PT)
	Electrocardiogram QRS complex prolonged (PT)
	Electrocardiogram QT prolonged (PT)
	Long QT syndrome (PT)
	Paroxysmal atrioventricular block (PT)
	Sinoatrial block (PT)
	Sinus bradycardia (PT)
AESI Coagulation related AEs	Blood fibrinogen decreased (PT)
	Blood thrombin decreased (PT)
	Blood thromboplastin abnormal (PT)
	Blood thromboplastin decreased (PT)
	Coagulation factor IX level decreased (PT)
	Coagulation factor V level decreased (PT)
	Coagulation factor VII level decreased (PT)
	Coagulation factor X level decreased (PT)
	Coagulation factor decreased (PT)
	Hypofibrinogenaemia (PT)
	International normalised ratio abnormal (PT)
	Prothrombin level decreased (PT)
	Prothrombin time prolonged (PT)
	Prothrombin time ratio decreased (PT)
	Thrombin time prolonged (PT)
AESI Gallbladder and biliary related AEs	Bile duct necrosis (PT)
	Bile duct obstruction (PT)
	Bile duct stenosis (PT)
	Bile duct stone (PT)

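### The gallbladder and biliary AESI group in SAP 8.2 has no cholangitis term, so the incidence reported for that group can be too low

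*SAP*

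**What the plan says.** SAP 7.4.1 makes the attachment the operative definition: "The specific categories of AEs of special interest list for SOM230 are listed in attachment 8.2". The same section has AESIs listed and summarised separately, for all grades and for grade 3 or 4 side by side. SAP 7.1.1 and protocol 10.5.3 name AESI, with AEs and SAEs, as a basis of the safety assessment.

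The group headed "AESI Gallbladder and biliary related AEs" opens with bile-duct terms, among them "Bile duct obstruction (PT" and "Bile duct stone (PT". (In the extracted text these first rows stand just above the 8.2 heading, but they belong to the AESI table.) Further down come "Cholangiogram abnormal (PT" and the cholecystitis terms, including "Cholecystitis acute (PT". Milder or less specific entries, such as biliary dyspepsia and an abnormal alkaline phosphatase, are also in the group.

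Protocol 2.6 lists, among the expected pharmacodynamic effects of pasireotide, "bradycardia, mild QT prolongations, cholelithiasis and transient elevations in serum levels of transaminases". Protocol 1.2.1.2.2 reports cholelithiasis in 20% and 45% of the two arms of a 12-month trial of the LAR formulation in Cushing's disease.

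**The concern.** An AESI group pools related preferred terms so that one incidence describes one kind of harm. This group counts inflammation of the gallbladder in three forms and counts stones, obstruction, narrowing and perforation of the bile duct. It does not count inflammation of the bile duct. No stated principle separates the two, and a reader of the biliary AESI figure would not know that cholangitis had been left out.

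The other listed terms will not always pick the patient up. Protocol 8.1.1 asks sites to report a diagnosis, where possible, in place of its signs and symptoms. Protocol 8.1.2.1 does not require a separate entry for a laboratory result that belongs to an event already reported. A case may thus arrive as cholangitis alone, without jaundice or a raised bilirubin. Protocol 8.1.1 also records AEs still ongoing from the parent study as medical history, so gallstones present at roll-over are not a new AE unless they worsen.

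At stake is the completeness of one descriptive incidence in the assessment of long-term safety, for an organ system in which the protocol already expects a drug effect.

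**Working it through.** The plan has no sample size, power or error rate to reproduce: protocol 10.7 marks sample size as not applicable, and SAP 7.1.2 tests no hypothesis. The check is a reading of the list, followed by the route of an event through the planned tables.

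**1. Search of the group.** The gallbladder and biliary group has 62 printed lines.
- Lines with the stem cholang: 1, the abnormal cholangiogram, which is an imaging finding.
- Lines for cholangitis: 0.
- Lines with infect or sepsis: 0.
- Lines with cholecystitis: 3 (unspecified, acute, chronic).
- Lines with obstruct: 5. Bile duct stone: 1.

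**2. Could the term have been lost in text extraction?** After three evident misreadings are corrected (haemobilia, hepatitis cholestatic, jaundice), the list is in alphabetical order throughout. Cholangitis would fall between line 27 (abnormal cholangiogram) and line 28 (cholecystectomy). The table's page breaks fall after lines 4 and 44, and the garbled lines begin at line 49. The stretch around lines 27 and 28 reads cleanly, and nothing suggests a lost row.

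**3. Other groups.** SAP 8.2 has 13 AESI groups. The other 12, including liver safety and pancreatitis, contain no cholangitis term.

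**4. Route of a treatment-emergent cholangitis event.**

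| What is coded in the roll-over | Biliary AESI group | General AE tables by SOC and PT | SAE or death tables |
|---|---|---|---|
| Cholangitis only | Not counted | Counted | Counted if serious or fatal |
| Cholangitis, with stones held as medical history | Not counted | Counted | Counted if serious or fatal |
| Cholangitis plus a listed term, such as bile duct stone or jaundice | Patient counted through the listed term | Counted | Counted if serious or fatal |

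**5. Size.** The documents give no cholangitis rate and no final Safety Set size, so the under-count cannot be computed. To show the order of magnitude only, three borrowed inputs can be combined:
- 301 patients, the enrolment stated in the Amendment 2 rationale of September 2017;
- 20% to 45% with cholelithiasis, from the one Cushing's trial in protocol 1.2.1.2.2;
- 1% to 3% of those developing cholangitis, which is purely an assumption.

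Low: 301 × 0.20 × 0.01 = 0.6 patients (0.2%). High: 301 × 0.45 × 0.03 = 4.1 patients (1.4%).

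The range moves in proportion to the assumed 1% to 3%. It also treats all indications and both formulations like that one trial, and any patient with a co-reported listed term would come off it.

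**The case against.** The strongest answer is that little is lost. SAP 7.4.1 tabulates every treatment-emergent AE by SOC and PT, with grade and relationship, and repeats this for SAEs. It adds tables for events leading to discontinuation, to dose adjustment or interruption, or to additional therapy. SAP 7.4.1 and 7.4.2 tabulate deaths by SOC and PT. The primary endpoint in SAP Table 5-1 is the frequency and severity of AEs and SAEs. This stands in full. A reader might infer from the gap that cholangitis goes uncounted in the safety analysis; the documents do not support that.

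Two further inferences also fail. The SAP plans no count of serious biliary AESIs, so none can be wrong. Nor does the group keep minor events and miss the most serious: it includes bile duct necrosis and perforation, gallbladder necrosis, biliary ischaemia and acute cholecystitis.

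The isolated case is also narrower than it may seem. Sites may report a bile duct stone beside cholangitis, stones that worsen after consent are a new AE under protocol 8.1.1, and protocol 8.2.2 treats complications of an SAE as follow-up to the original event. This limits the number affected but does not bring it to zero.

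Lastly, protocol 8.1.3 says that AESIs come from ongoing safety review and are discussed in the Investigator Brochure, which is not available here. The group has no infection or sepsis term at all, so a deliberate choice of scope cannot be excluded. That tells against calling the omission a proven mistake. It does not remove the gap, because the SAP states no principle that would include cholecystitis and leave out cholangitis.

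**Conclusion.** The point holds within a limited scope. As written, SAP 8.2 leaves out of the biliary AESI incidence any patient whose only treatment-emergent biliary event is coded as cholangitis. The effect is an under-count in one descriptive grouping, with the event still visible in other planned tables.

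The size cannot be derived from the documents and is probably a few patients at most. The 0.6 to 4.1 in the illustration should not be cited as an estimate.

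The conclusion assumes that cholangitis is a separate PT in the MedDRA version used, which the coding team must confirm. That cholangitis can complicate stones or obstruction is general clinical knowledge and is not stated in the documents; the gap is visible from the list's own contents without it. The change is worth making because AESI is a named part of the safety assessment and the correction is nearly free, though its numerical effect will be small.

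**What to change.** In SAP 8.2, add to the gallbladder and biliary group the cholangitis PTs that exist in the MedDRA version used for the analysis. Check related biliary-infection PTs at the same time, and rerun the AESI flag. SAP 7.4.1 calls for the latest available MedDRA version while 8.2 names none, so a check of the list against that version is useful in any case. If the omission is intended, state the reason in 8.2.

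Do this before database lock, by which time SAP section 2 requires decisions on the final analysis to be made; terms added later could look data-driven.

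The cost is a few lines in an attachment and one rerun, with no new data. The downside is that the biliary AESI percentage may rise slightly and may differ a little from earlier interim reports that used the old list. A footnote to the AESI table can say so.

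### Obstructive pancreatitis is listed only in the gallbladder AESI group, so the pancreatitis AESI total omits it; the low-blood-cell group has a similar, less certain gap (minor)

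*SAP*

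**What the plan says.** SAP 7.4.1 has AESIs listed and summarised as a selection of their own and refers to attachment 8.2 for the categories. SAP 7.1.1 makes AESI frequency and severity part of the primary safety assessment, alongside AEs and SAEs. SAP 7.1.2 keeps this descriptive, with no hypothesis test.

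Attachment 8.2 is a list of PTs by category. Three categories matter here:

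- **Gallbladder and biliary.** This contains "Obstructive pancreatitis (PT", the only place the term occurs in either document.
- **Pancreatitis**, headed "AESI Pancreatitis related AEs". Its pancreatitis diagnoses run from the unspecified term to "Pancreatitis relapsing (PT". The rest are enzyme findings and related conditions.
- **Low blood cell**, headed "AESI Low blood cell related AEs". It includes "Leukopenia (PT" and "Lymphocyte count decreased (PT". Neutrophils appear only as a condition ("neutropenia (PT", with and without the febrile qualifier).

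**The concern.** A row labelled pancreatitis should hold every pancreatitis diagnosis that the sponsor has put on its own list. Here one such diagnosis is on the list but is sent only to another category. Nothing in the SAP adds unlisted PTs to a category, so a programmer following the attachment would leave these patients out of the pancreatitis row.

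The low-blood-cell list raises a similar question. For three cell lines it anticipates that an event may be coded either as a condition or as a laboratory decrease. For neutrophils and total white cells it anticipates only the condition. If MedDRA has corresponding count PTs, an event coded that way would fall outside the category.

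The study is a long-term safety study with descriptive output, also classed as a voluntary post-authorisation safety study. Its category counts will be read at face value as results, so they should match their labels.

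**Working it through.** No power, alpha or sample-size figure is involved, and the plan states no number to reproduce. The check is one of list membership in attachment 8.2.

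**1. Pancreatitis category.** Its 15 PTs are: Abdominal compartment syndrome, Blood trypsin increased, Fat necrosis, Hyperlipasaemia, Lipase abnormal, Lipase increased, Pancreatic enzyme abnormality, Pancreatic enzymes abnormal, Pancreatic enzymes increased, Pancreatitis, Pancreatitis acute, Pancreatitis haemorrhagic, Pancreatitis necrotising, Pancreatitis relapsing, Peripancreatic fluid collection. Five are pancreatitis diagnoses. The obstructive form is absent.

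**2. Low-blood-cell category.** It has 11 PTs, grouped here by cell line:

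| Cell line | Condition term | Count or laboratory term |
|---|---|---|
| Red cells | Anaemia | Red blood cell count, Haemoglobin, Haematocrit decreased |
| Platelets | Thrombocytopenia | Platelet count decreased |
| Lymphocytes | Lymphopenia | Lymphocyte count decreased |
| Neutrophils | Neutropenia, Febrile neutropenia | none |
| Total white cells | Leukopenia | none |

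That is 6 condition terms and 5 laboratory terms, 6 + 5 = 11. None of the 11 names a neutrophil count or a total white-cell count.

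**3. Could text have been lost in the PDF?** This is unlikely. Both lists run in alphabetical order, and no repeated table header falls where the missing terms would sit.

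**4. Does the SAP allow only one category per PT?** No. Electrocardiogram QT prolonged and Long QT syndrome are in both the bradycardia and QT categories. Urine bilirubin increased is in both the gallbladder and liver categories. Listing a term twice is already the SAP's practice.

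**5. Who is affected?** For the pancreatitis row, only a patient who has the obstructive PT and none of the 15 listed PTs. A patient who also has, say, Lipase increased is already counted. For the low-blood-cell row, only a patient whose event is coded to a neutrophil-count or total white-cell-count PT and who has none of the 11 listed PTs.

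**6. Size.** The documents contain no event counts for these terms, so the change in either total cannot be computed. The lists themselves would grow from 15 to 16 PTs and, if both count terms exist, from 11 to 13.

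**The case against.** The strongest reply is that nothing disappears. Obstructive pancreatitis is still an AESI under gallbladder, and SAP 7.4.1 tabulates all treatment-emergent events by system organ class and PT. With no hypothesis test, no decision rule depends on a category total. Protocol 8.1.3 also says AESIs come from ongoing safety review and are discussed in the Investigator Brochure, so the placement may be a deliberate medical grouping. All of this limits the consequence, and it is why the point is minor. It does not explain why a category holding five pancreatitis diagnoses leaves out a sixth that the attachment names, when listing a term in two categories is allowed.

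The low-blood-cell point is weaker. Protocol 8.1.1 and 8.1.2.1 ask sites to report a diagnosis rather than a laboratory finding where they can, which narrows the gap. It does not close it, because 8.1.2.1 still allows a laboratory abnormality to be an AE in its own right, and the list includes laboratory terms for other cell lines. Whether matching PTs exist for neutrophils and white cells is not shown in the documents.

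A reader might infer more, and four stronger readings should be resisted:

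- **That neutrophil and white-cell events are lost as a class.** Those coded as Neutropenia, Febrile neutropenia, Leukopenia, Lymphopenia or Lymphocyte count decreased are all captured.
- **That the omitted form is the one most relevant to this drug.** Protocol 1.2.1.2.2 does report "cholelithiasis (15 [20%] and 34 [45", meaning 20% and 45% in the 10 mg and 30 mg groups of SOM230G2304. Neither document links gallstones to obstructive pancreatitis or says how such cases would be coded.
- **That the pancreatitis total is understated by some stated percentage.** Any such figure needs an assumed number of other cases and an assumed obstructive case. It must also allow for no obstructive case at all and for the enzyme terms already in the category. The 301 patients given in the Amendment 2 rationale are enrolment at that time, not the final Safety Set.
- **That Table 14-12 shows low neutrophil counts will be missed.** That table applies to patients from SOM230D2101, a study not in SAP Tables 2-1 or 2-2, and it labels the low count as neutropenia, which is on the list.

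**Conclusion.** The pancreatitis point holds on the face of attachment 8.2. As written, a patient whose only pancreatitis-type event is coded as obstructive counts under gallbladder but not in the pancreatitis total. It rests on one reading: that category membership is set by the attachment alone, which is what SAP 7.4.1 indicates.

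The low-blood-cell point is secondary and conditional. The asymmetry in the list is a fact, but it has an effect only if the count PTs exist in the MedDRA version used and events are coded to them.

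Both affect AESI category totals only. The overall AE and SAE analysis is not threatened. The undercount is unknown, probably small and possibly zero. Severity is minor.

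**What to change.** Before database lock, which is when SAP section 2 says decisions on the final analysis will have been made:

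1. Add Obstructive pancreatitis to the pancreatitis category in attachment 8.2 and leave it under gallbladder as well.
2. Check the MedDRA version used for the analysis for PTs denoting a decreased neutrophil count and a decreased total white-cell count. Add those that exist to the low-blood-cell category. If none exist, no change is needed.
3. If the present placement of the obstructive term is intended, say so in a footnote to the AESI table so that the pancreatitis row is not read as complete.

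The cost is one certain entry and up to two conditional ones in the attachment, with the matching change to the AESI grouping in the programs. No new data are needed. The two category counts can only stay the same or rise.
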